- All TEAEs by treatment group regardless of relationship in one column and, in the same table a second column with TEAEs related to alirocumab according to investigator's opinion by primary SOC, HLGt, HLT and PT;
- All TEAEs by maximal severity (i.e., mild, moderate or severe), presented by primary SOC and PT, sorted as defined above;
- The event rate per patient-year (the number of patients with an event in question divided by total patient-years) will be provided for all TEAEs by SOC and PT. For a patient with event, patient year is censored at time of first event; for patient without event, it corresponds to length of TEAE period;
- Kaplan-Meier curves will be provided, when appropriate, for time from first dose of study treatment to the first occurrence of selected TEAEs as well as incidence rates at 24, 48, 72, and 96 weeks of exposure. Patients without any event will be censored at the end of the TEAE period. Selected TEAEs could be AESIs (e.g. neurocognitive events), or TEAE related to any clinically significant signal that needs further characterization;

- The frequency of selected AEs by SOC and PT over time during the treatment period (number of patients experiencing AE and percentage by patient-months) will be provided by time intervals defined as: ≤ 24 weeks, >24 to ≤ 48 weeks, >48 to ≤ 72 weeks, >72 to ≤ 96 weeks, using the PROC LIFETEST with the actuarial method. Only the first event will be counted.

Analysis of all treatment emergent serious adverse event(s)

- All serious TEAEs by primary SOC, HLT, HLT, and PT and by SOC/PT; Patient listings of serious TEAEs will be provided for the report appendix.
- All serious TEAEs by treatment group regardless of relationship in one column and in the same table a second column with TEAEs related to alirocumab according to investigator's opinion, by primary SOC, HLT, HLT, and PT;
- The event rate per patient-year will be provided for all serious TEAEs by SOC and PT.

Analysis of all treatment-emergent adverse event(s) leading to treatment discontinuation

- All TEAEs leading to permanent treatment discontinuation, by primary SOC, HLT, HLT, and PT and by SOC/PT; Patient listings of TEAEs leading to permanent treatment discontinuation will be provided for the report appendix.

Analysis of groupings of adverse events including selected adverse events of special interest

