- All grouping of TEAEs including adverse events of special interest, as listed in Section 4.7.1.2, will be presented by SMQ/CMQ and PT (when selection is based on SMQs/CMQs) and by SOC and PT (when selection is based on the e-CRF tick box or HLT/HLT). The summaries will be sorted by decreasing incidence of PT within each SOC/SMQ (in the Praluent group).
- Neurocognitive events adjudicated by the neurocognitive events review committee will also be summarized by primary SOC and PT. They will also be summarized according to the adjudication of possible etiology of the neurocognitive events (Yes/No) (Section 4.7.1.2).
- All TEAEs within diabetes grouping will be analyzed overall and according to the diabetic status at baseline (i.e., in patients With and without diabetes at baseline).

The following variables will also be tabulated for the local injection site reactions TEAEs:

- Intensity of the event (mild, moderate, severe);
- Number of events divided by the number of study treatment injections received;

- Time from first study treatment injection to first injection site reaction;
- Description of the highest intensity of each symptom recorded in the specific e-CRF page with table and bar chart.

Description of symptoms and possible etiologies for General Allergic Reaction TEAE reported by investigator (using the tick box), will be presented.

Post-treatment adverse events

- All post-treatment AEs by primary SOC and PT, sorted by the internationally agreed SOC order and decreasing incidence of PTs (in the Praluent group) within each SOC;
- All post-treatment SAEs by primary SOC and PT, sorted by the sorting order defined above.

Subgroup of patients with two consecutive LDL-C <25 mg/dL (<0.65 mmol/L) and LDL-C <15 mg/dL (< 0.39 mmol/L)

If applicable, similar summaries of TEAEs as those described above will be provided on the safety subgroup population of patients with two consecutive results of LDL-C <25 mg/dL (as defined in Section 4.8) in both treatment groups. Only TEAEs for which it will be confirmed or unclear that they occurred, worsened or became serious on the day or after the day the first level of LDL-C <25 mg/dL was observed will be considered in this summary.

In addition, the neurocognitive event rate in patients with 2 consecutive results separated by at least 21 days, and with only 1 such event for calculated LDL-C <25 mg/dL, and calculated LDL-C <15 mg/dL, will be assessed.

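### In the subgroup with two consecutive LDL-C values <25 mg/dL, TEAEs count only from the first low value but patient-years run from the first injection, so rates per patient-year are biased low

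*SAP*

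**What the plan says.** SAP 5.7.1 plans, where applicable, that "similar summaries of TEAEs as those described above will be provided on the safety subgroup population of patients with two consecutive results". The threshold is an LDL-C below 25 mg/dL. Membership is defined in SAP 4.8: two consecutive results at least 21 days apart during the treatment period, which SAP 4.7.1 ends 21 days after the last injection. Events are restricted: a TEAE enters the summary only if it is known to have, or may have, "occurred, worsened or became serious on the day or after the day the first level of LDL-C <25 mg/dL was observed".

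The summaries carried over include a rate per patient-year for all TEAEs and another for serious TEAEs. Their person-time is defined once, earlier in SAP 5.7.1. If the patient had an event, "patient year is censored at time of first event". If there was none, the rule reads "for patient without event, it corresponds to length of TEAE period". SAP 4.7.1 starts the TEAE period at the first injection and ends it 70 days after the last. No sentence gives the subgroup a different start for person-time.

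The subgroup heading also names LDL-C <15 mg/dL, but the event rule mentions only <25 mg/dL. A separate sentence, also in Protocol 9.5.2.6, plans "the neurocognitive event rate in patients with 2 consecutive results separated by at least 21 days" without giving a start date, an onset rule or a denominator.

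**The concern.** Numerator and denominator start on different dates. From the first injection to the first low LDL-C value, a patient adds person-time to the rate but cannot add an event known to have begun then. This is a form of immortal-time bias, and it pulls the rate down.

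Protocol 1.1 says that clinical data on very low circulating LDL and neurocognitive function are limited, so safety results at very low LDL-C will be read closely. A reader will naturally set the subgroup's rate beside the rate in the whole safety population, which has no such event-free lead-in. Very low LDL-C could then look safer through arithmetic alone, and in a safety summary that is the non-conservative direction.

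**Working it through.** The documents give no figure for this rate, so there is none to reproduce. The check compares the rate as written with the true rate after the first low value.

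**Inputs from the documents**
- Last dose at week 94 (Protocol 3.1) and a TEAE period ending 70 days later (SAP 4.7.1). For a completer, T = 94 × 7 + 70 = 728 days, or 104 weeks.
- Scheduled lipid time points at weeks 8, 12, 24, 48, 72 and 96 (SAP 5.6.3.1). With scheduled draws only, the first of two low values can fall at week 8, 12, 24, 48 or 72.

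**Assumptions:** the timing of first low values and the true event rate are not in the documents, so both are shown as ranges.

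**Rare event.** Events accrue over T − t, where t is the time to the first low value, but person-time accrues over T. The ratio of reported to true rate is (T − t)/T. At week 24, (728 − 168)/728 = 560/728 = 0.77.

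**Common event.** With constant hazard h, let D = 1 − exp(−h(T − t)), with times in years. The rate as written is D/(D/h + t). For h = 1 per patient-year and week 24: T − t = 560/365.25 = 1.533, D = 0.784, t = 168/365.25 = 0.460, and the rate is 0.784/(0.784 + 0.460) = 0.63.

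| First low value | Rare event, T = 728 days | h = 1 per patient-year, T = 728 days | Rare event, T = 672 days |
|---|---|---|---|
| Week 8 | 0.92 | 0.85 | 0.92 |
| Week 12 | 0.88 | 0.78 | 0.88 |
| Week 24 | 0.77 | 0.63 | 0.75 |
| Week 48 | 0.54 | 0.42 | 0.50 |
| Week 72 | 0.31 | 0.25 | 0.25 |

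The last column cuts person-time at week 96, because Protocol 8.2.5 collects adverse events to the end-of-study visit.

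**Assumed timing mixes.** The table shows the share of patients with a first low value at weeks 8/12/24/48/72, with T = 104 weeks and a rare event.

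| Mix (%) | Mean t (weeks) | Ratio | A true 5.0 per 100 patient-years is reported as |
|---|---|---|---|
| 60/20/15/3/2 | 13.68 | 90.32/104 = 0.87 | 4.3 |
| 20/10/50/10/10 | 26.8 | 77.2/104 = 0.74 | 3.7 |
| 20/20/20/20/20 | 32.8 | 71.2/104 = 0.68 | 3.4 |

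**Aligned start.** A simulation of 2,000,000 patients per mix started person-time at the first low value. The ratio returned to 0.997 to 1.002 for events that do not prevent a second measurement.

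**Second-value condition.** As an extreme case, suppose every event between the two values prevents the second one. Person-time from the first low value then still gives 0.89, 0.75 and 0.75 in the three mixes. Starting events and person-time at the second value gives 0.998 in each. The true share of such events is unknown, so these figures bound the effect and do not estimate it.

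**The case against.** **The mismatch is inferred.** The subgroup text says similar summaries, if applicable, and does not restate a denominator. A programmer might choose a sensible start date. That is fair, but the only written patient-year rule is the one for the full TEAE period, and SAP section 1 says that the plan exists to specify methods before unblinding.

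**Most outputs are not affected.** A reader might infer that the whole subgroup safety display is biased by this rule. It is not: the n (%) tables use no patient-years. The effect is on the two rates per patient-year and on any Kaplan-Meier curve timed from first dose, if one is repeated for the subgroup.

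**The neurocognitive event rate.** A reader might infer that it has the same fault. The documents do not show that. It stands in a separate sentence with no onset restriction, so under the default rule events and time would both cover the full TEAE period. It may also simply mean a percentage, since Protocol 9.5.2.6 summarises these events by number and percentage. What stands is that it is undefined.

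**Loss of patients who stop drug.** A reader might infer that someone who has an event and stops treatment will hardly ever show a second low value, and so add a further large bias. Protocol 7.3.1 asks for a visit with end-of-study assessments, within 5 days of stopping if possible. Table 1 includes the lipid panel at that visit, and SAP 6.6 allows unscheduled values. Such a patient can qualify if that value is low and comes at least 21 days after the first. Any figure for this loss rests on an assumed exit probability. The dependence on a later value is real; its size is not known.

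**Other limits.** Safety summaries carry no formal testing (SAP 5.7). SAP 5.6.2 separately plans SWM strategy scores in the same LDL-C groups, so this rate is not the trial's only look at the question. Counting TEAEs of unclear timing pushes the rate up by an amount that cannot be computed from the documents.

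**Conclusion.** The point holds for the rates per patient-year of all TEAEs and of serious TEAEs in the subgroup with two consecutive values <25 mg/dL. Followed literally, the SAP biases them low in every scenario computed. For a completer with a rare event, the shortfall is 8% if the first low value is at week 8, 23% at week 24 and 46% at week 48. Under the three assumed mixes it is between about 13% and 32%.

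The conclusion rests on reading the carried-over summaries as bringing their patient-year rule with them, and on a 104-week TEAE period. The direction does not depend on the assumed timing, but the size does. It is worth correcting before database lock, because it errs in the reassuring direction and is easy to remove. It does not touch the primary analysis.

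**What to change.** In SAP 5.7.1, state that in this subgroup patient-years, and the time origin of any Kaplan-Meier curve, start on the date from which events are counted: the first low LDL-C value. Write the same rule for the <15 mg/dL group with its own threshold. Say whether the neurocognitive event rate is a percentage or a rate per patient-year; if the latter, apply the same start to its events and person-time.

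Add a sensitivity analysis that starts both events and person-time at the second qualifying value, since membership depends on that value and events that prevent it are lost from the main rate.

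The cost is a few sentences and a re-dating of data already held. In the sensitivity rate, events between the two values drop out. As an illustration, with first low values at weeks 8/12/24/48/72 in 30/20/30/15/5% of patients (assumed), the mean scheduled gap to the second value is 1.2 + 2.4 + 7.2 + 3.6 + 1.2 = 15.6 weeks. The mean time from first low value to week 104 is 104 − 22.8 = 81.2 weeks, so about 19% of post-low time is set aside. For that reason the second-value start should stay a sensitivity analysis, and the time set aside should not be reassigned to a comparator labelled as not low: it follows a documented low value.

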5.7.1.1. Patient Deaths

The following summaries of deaths will be generated.

- Number (%) of patients who died by study period (TEAE and post-treatment);
- Deaths in nonrandomized patients or randomized but not treated patients;
- TEAEs leading to death (death as an outcome on the AE CRF page, as reported by the Investigator) by (at least) SOC (sorted by internationally agreed order), and PT (sorted by decreasing frequency, showing the number (n) and percentage (%) of patients) for the safety population.

5.7.2. Analysis of Clinical Laboratory Variables

Clinical laboratory parameter actual values (quantitative) and change from baseline values will be descriptively summarized at baseline and each post-baseline visit (collected up to the

day of last dose of study treatment +21 days) by at least patient number, mean, median, Q1, Q3, SD, minimum and maximum for each treatment group. Additionally, laboratory parameter measures for last on-treatment values and worst on-treatment values will be summarized in a similar manner. Clinical laboratory parameters mean changes from baseline, with the corresponding SE, can be plotted at each visit by treatment group, in the case results warrant further investigation. These parameters will be presented by the biological functions defined in Section 4.7.2. For glucose, only fasting samples will be included in the summaries.

Individual patient laboratory parameter measurements will be additionally evaluated by PCSA criteria, specifically identifying patients with at least one post-baseline measurement that meets the PCSA criteria within the TEAE period. The following additional project specific PCSA criteria will also be evaluated during the TEAE period:

- Patients with a hemoglobin decrease from baseline ≥ 15 g/L.
- Patients meeting the ALT increase defined in Section 4.7.1.2.

Glucose (quantitative summary and PCSA) will also be analyzed, overall and according to the diabetic status at baseline.

Patients meeting the PCSA criteria at least once will be summarized by patient count (and percent) for a post-baseline PCSA measurement while accounting for the baseline PCSA status (PCSA normal/missing; PCSA abnormal), for each treatment group. For the appendix, this laboratory parameter PCSA table will be reproduced with patients meeting the PCSA criteria at least once during the TEAE period regardless of baseline PCSA status. These laboratory parameters will be presented by the biological functions defined in Section 4.7.2. Patient listings of laboratory measurements that meet PCSA criteria will be provided for the report appendix. For those laboratory parameters that don't have an associated PCSA criteria, similar summary tables can be provided based on measurements outside the central laboratory normal ranges, if applicable.

Hepatitis C antibody

The number and percentage of patients with a post-baseline seroconversion for hepatitis C test will be provided by treatment group in post-baseline (including the TEAE and post TEAE periods) as well as in the TEAE period alone. Post-baseline seroconversion is defined for patients with a negative baseline status who had either a “positive RNA” or a “confirmed positive antibody with negative RNA” post-baseline status as defined in the table below. Other situations require case by case evaluation and will be described individually if relevant.

The status as regards hepatitis C virus for a patient will be defined as follows for all evaluations (baseline and post-baseline).

Table 1: Definition of the patient status regarding hepatitis C virus

		Hepatitis C Antibody test result			
		Negative		Positive	
Reflexive test ^a – hepatitis C RNA test	Not available or HCV RNA not detected	HCV RNA detected	HCV RNA not detected ^b	HCV RNA detected	Not available
Hepatitis C status – label	Negative	Positive RNA	Negative ^b	Positive RNA	Positive Ab – no RNA available

^a test performed at the same time or after the antibody test in pre-treatment period (for baseline evaluation), or post-baseline, respectively

^b For post-baseline evaluation, a second antibody test with a different type of assay is to be done at the same date or after the first antibody test. The result of this test will modify the final hepatitis C status of the patient in some cases (see details in the text below the table)

The baseline evaluation will be based on tests performed during the pre-treatment period.

In case of multiple hepatitis C tests available for the post-baseline evaluation, the positive status of the patient will be defined as follows:

- “Positive RNA” status if at least 1 post-baseline positive RNA is detected, regardless of status of the patient at the end of treatment.
- Else “Positive Ab – no RNA available” status if no post-baseline reflexive RNA test is available for at least 1 post-baseline positive antibody test.

If no antibody test is available or with “indeterminate” as result pre-treatment or post-baseline respectively, the RNA test (if available) will be used alone to determine the status of the patient. If no RNA test is available then the hepatitis C status of the patient will be missing.

The post-baseline status “confirmed positive antibody with negative RNA” will replace “Negative” status as defined above in the case where no RNA was detected post-baseline and the 2 antibody tests surrounding the same visit (from 2 different types of assay) are positive.

For a conservative approach, the post-baseline status “Positive Ab – no RNA available” will not be modified by the availability of a second antibody test from a different assay.

For the description of the positive hepatitis C virus test during the TEAE period, all above rules will apply while replacing post-baseline by TEAE period.

Drug-induced liver injury

The liver function tests, namely AST, ALT, ALP, and total bilirubin, are used to assess possible drug-induced liver toxicity. The proportion of patients with PCSA values or ALT increase as defined as AESI (see Section 4.7.1.2) during TEAE period by baseline status will be displayed by treatment group for each parameter.

An evaluation of drug-induced serious hepatotoxicity (eDISH) with the graph of distribution of peak values of ALT versus peak values of total bilirubin will also be presented using post-baseline values during TEAE period. Note that the ALT and total bilirubin values are presented on a logarithmic scale. The graph will be divided into 4 quadrants with a vertical line corresponding to $3 \times \text{ULN}$ for ALT and a horizontal line corresponding to $2 \times \text{ULN}$ for total bilirubin.

Listing of possible Hy's law cases identified by treatment group (i.e., patients with any elevated $\text{ALT} > 3 \times \text{ULN}$, and associated with an increase in bilirubin $> 2 \times \text{ULN}$, concomitantly or not) with ALT, AST, ALP, total bilirubin, and if available direct and indirect bilirubin will be provided.

The incidence of liver-related TEAEs will be summarized by treatment group. The selection of PTs will be based on SMQ Hepatic disorder (see Section 4.7.1.2).

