9.5.2.7. Laboratory Data and Vital Signs

The following definitions will be applied to laboratory parameters and vital signs:

- The baseline value is defined as the last available value before first dose of study treatment.
- The PCSA values are defined as abnormal values considered medically important by the sponsor according to predefined criteria/thresholds based on literature review and defined by the sponsor for clinical laboratory tests and vital signs.
- The PCSA criteria will determine which patients had at least 1 PCSA during the TEAE period, taking into account all evaluations performed during the TEAE period,

including unscheduled or repeated evaluations. The number of all such patients will be the numerator for the PCSA percentage.

- Treatment period: the treatment period used for quantitative analysis (laboratory results and vital signs) is defined as the time from first dose of study treatment to the last dose of study treatment + 21 days.

Summary statistics (including mean, median, Q1, Q3, standard error, minimum and maximum) of all laboratory variables and all vital sign parameters (raw data and changes from baseline) will be calculated for each visit, last and worst value assessed during the treatment period, and presented by treatment group. For selected parameters, mean changes from baseline with the corresponding standard error will be plotted over time (at same time points) in each treatment group.

The incidence of PCSAs at any time during the TEAE period (on-treatment PCSAs) will be summarized by treatment group, whatever the baseline level and/or according to the following baseline categories:

- Normal/missing
- Abnormal according to PCSA criteria

For laboratory parameters for which PCSA criteria is not defined, similar table(s) using the normal range could be provided.

Hepatitis C Test

The number and percentage of patients with an observed seroconversion for hepatitis C test will be provided by treatment group.

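### The hepatitis C seroconversion rule can count a patient whose antibody-positive, RNA-negative serology has not changed since before the first dose

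*SAP*

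**What the plan says.** Protocol Section 9.5.2.7 promises the summary: "The number and percentage of patients with an observed seroconversion for hepatitis C test will be provided by treatment group". SAP Section 5.7.2, under the hepatitis C antibody heading, defines how it is derived.

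- **Definition.** "Post-baseline seroconversion is defined for patients with a negative baseline status who had either a" 'positive RNA' status or a 'confirmed positive antibody with negative RNA' status after baseline. Situations outside this definition go to case-by-case evaluation.
- **Status table.** "The status as regards hepatitis C virus for a patient will be defined as follows for all evaluations (baseline and post-baseline"), so one table serves both time points. In Table 1, a positive antibody test with the reflex result "HCV RNA not detected" is labelled 'Negative', with footnote b attached.
- **Footnote b.** "For post-baseline evaluation, a second antibody test with a different type of assay is to be done" on or after the date of the first antibody test, and its result may change the final status.
- **Replacement rule, in the text after the table.** The post-baseline 'Negative' becomes 'confirmed positive antibody with negative RNA' when "no RNA was detected post-baseline and the 2 antibody tests surrounding the same visit (from 2 different types of assay) are positive".
- **Baseline.** "The baseline evaluation will be based on tests performed during the pre-treatment period". No second assay is mentioned for this evaluation.
- **Missing or indeterminate antibody.** The RNA result alone then sets the status.

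SAP Section 4.7.2 places the antibody test at week -3 and week 96. The summary is produced for the whole post-baseline period and again for the TEAE period.

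**The concern.** Seroconversion should mean that antibody or virus appeared after the first dose. The rule compares a baseline status with a post-baseline status, but the two are built differently: a positive antibody with undetected RNA is always 'Negative' at baseline, yet after baseline it can be upgraded by a second assay. Someone with past, cleared infection can move from one label to the other with identical blood results.

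Such patients can be enrolled. Protocol Section 4.2.2 excludes a positive HIV test and Child-Pugh Class C impairment, but not a positive hepatitis C antibody. SAP Section 4.1 lists hepatitis C antibody among the baseline disease characteristics, and Table 1 provides baseline labels for antibody-positive patients, so the plan expects some. At stake is whether the table reports new findings on study or mixes them with serology that was present at screening.

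**Working it through.** There is no stated figure to reproduce; the check is of a decision rule. Applying Table 1, footnote b and the replacement rule to each combination of results gives:

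| Baseline antibody / RNA | Baseline status | Later antibody / RNA / second assay | Post-baseline status | Counted? |
|---|---|---|---|---|
| Negative / not detected or not available | Negative | Positive / not detected / positive | Confirmed positive antibody with negative RNA | Yes, a real change |
| Positive / not detected | Negative | Positive / not detected / positive | Confirmed positive antibody with negative RNA | **Yes, nothing changed** |
| Positive / not detected | Negative | Positive / not detected / negative or not done | Negative | No |
| Positive / not detected | Negative | Positive / not available / positive | Positive Ab – no RNA available | No |
| Positive / not detected | Negative | Positive / detected / positive | Positive RNA | Yes, a new RNA finding |
| Positive / not available | Positive Ab – no RNA available | Any | Any | No |
| Positive / detected | Positive RNA | Any | Any | No |

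The second row is the defect. Comparing it with the sixth shows the inconsistency: the baseline antibody result is the same, and only the running of a baseline RNA test decides whether the patient can be counted.

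The clause on other situations does not help. The second-row patient satisfies the stated definition and would be counted by program before any case review.

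A related gap lies in the rule for a missing or indeterminate antibody. With undetected RNA such a patient is 'Negative' at baseline without any baseline antibody result, and can later be counted through the confirmed-antibody route.

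**Effect of the change.** If the confirmed-antibody route requires a negative baseline antibody, the second row moves from counted to not counted. The first row is still counted, and the fifth is unaffected.

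**Size.** The documents give no hepatitis C prevalence, so every input below except the planned 2170 patients is an assumption:

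count = 2170 × (antibody positive at baseline) × (RNA negative among them) × (retested at week 96) × f1 × f2 × f3

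Here f1 is the share with a baseline RNA test, f2 the share with a post-baseline RNA test that again detects nothing, and f3 the share with a second assay done and positive. With f1 = f2 = f3 = 1:

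- low inputs: 2170 × 0.005 × 0.30 × 0.60 = 2.0 patients (2.0 / 2170 = 0.1%);
- high inputs: 2170 × 0.02 × 0.80 × 0.90 = 31.2 patients (31.2 / 2170 = 1.4%).

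Each f is at most 1, so these are upper-end values and the lower one could fall close to zero. SAP Table 1 itself provides for RNA results that are not available. The protocol's Schedule of Events and Section 7.6.4.3 name only the hepatitis C antibody, not an RNA test or a second assay.

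**The case against.** The strongest reply is that the consequence is small and needs several conditions at once. RNA must be run and not detected at both time points, and a second assay of a different type must be done and be positive. A reader might infer that any unchanged positive antibody at week 96 is counted; the table above shows that it is not. This limit stands. It does not remove the defect, because a positive second assay is the expected result in a patient with genuine persistent antibody.

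It is also fair to say that enrolment of such patients may be uncommon. Protocol Section 7.6.1 lists hepatitis C antibody among tests used for eligibility or for characterizing the baseline population, and exclusion criterion 11 leaves room for investigator judgement. Neither bars these patients, and how many enter is unknown.

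The impact is limited too. SAP Section 5.7 rules out formal inferential testing of safety data, hepatitis C is not among the adverse events of special interest in SAP Section 4.7.1.2, and 1:1 randomization should place these patients in both arms. Baseline antibody status is tabulated by arm, so a reader could see that some patients were already positive, though not whether they are the ones counted as seroconverters.

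A deliberately conservative rule is a weaker defence. The SAP uses that word only for leaving the label for a positive antibody without RNA unmodified, and conservatism would not explain why the baseline RNA test decides who can be counted.

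**Conclusion.** The concern holds in a limited form. As written, the rule can count unchanged serology as seroconversion, and it treats the same baseline antibody result differently according to whether RNA was tested. This follows from the SAP text and needs no assumption about prevalence.

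The number affected cannot be computed from the documents. The range of 2 to 31 is an upper-end illustration on assumed inputs, not an estimate. A reader might infer that false cases would dominate the table or create a between-arm signal. The documents support neither: they give no rate of true seroconversion and no prevalence, and the excess is expected in both arms, leaving only chance imbalance.

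The error is confined to one descriptive safety summary in its two versions and does not touch the primary neurocognitive analysis. Severity is minor.

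**What to change.** In SAP Section 5.7.2, before database lock:

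1. Count 'confirmed positive antibody with negative RNA' as seroconversion only in patients with a negative hepatitis C antibody test at baseline.
2. List separately the patients who are antibody positive with undetected RNA at baseline, with their later results.
3. State that patients whose baseline antibody is missing or indeterminate go to case-by-case review for this route.
4. Leave the 'positive RNA' route as written, but flag any case that was antibody positive at baseline. Taking such cases out of the count would be a choice of definition that this defect does not require.

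The cost is a few sentences and a small change to the derivation. No new data are needed, because Table 1 already uses the baseline antibody and RNA results.
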